**Table 3: Primary and Sensitivity Analyses of Primary Endpoints**

Endpoint	Statistical Method	Analysis Population	Primary (P) or Supportive (S)
Proportion of participants who have died due to any cause through Study Day 29.	Logistic regression with treatment group and ARDS severity (severe vs mild/moderate) as fixed covariates, and investigational site as a random effect. Wald test for treatment group regression coefficient = 0.	ITT	P
	Estimation: Odds-ratio for treatment effect and associated 95% CI.	PP	S
	Logistic regression with treatment group and ARDS severity (severe vs mild/moderate) as fixed covariates, and investigational site as a random effect, treating participants who are lost to follow-up before Day 29 as deaths.	ITT	S
	Logistic regression with treatment group and ARDS severity (severe vs mild/moderate) as fixed covariates, and investigational site as a random effect using actual PaO 2 /FiO 2 at Day 1 (as entered into eCRF).	ITT	S
	Logistic regression with treatment group, ARDS severity (severe vs mild/moderate), and gender (male or female) as fixed covariates, and investigational site as a random effect. Wald test for treatment group regression coefficient = 0.	ITT	S

The 28-day mortality rates and participants lost to follow-up in the placebo group will be compared by the placebo image assigned (5 mg BID and 15 mg BID) to determine if the rate is consistent across the 2 treatment images. Statistical comparisons between the 2 images will be performed using a Fisher's exact test in all placebo-assigned participants and within ARDS

severity subgroup. Additional endpoints may also be compared within placebo-assigned participants by treatment image.

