bronchitis, and the possibility of developing anemia, bleeding, fatigue, and/or shortness of breath. In healthy volunteers, rheumatoid arthritis patients, and patients with pancreatic cancer or hormone-refractory prostate cancer, the effects on hematopoietic proliferation are less pronounced, presumably because of greater bone marrow reserve. The most frequent nonhematologic AEs were mild, reversible increases in ALT and AST; bruising; hypercholesterolemia; dizziness; headache; and urinary tract infections. Tuberculosis has been infrequently reported in patients receiving ruxolitinib to treat MF (< 1/100 patients). The symptoms of tuberculosis include chronic cough with blood-tinged sputum, fever, night sweats, and weight loss. There may be risks associated with rapid discontinuation of ruxolitinib.

Patients with MF, particularly those who have stopped taking ruxolitinib suddenly after long-term administration, have reported return of MF symptoms such as fatigue, bone pain, fever, pruritus, night sweats, symptomatic splenomegaly, and weight loss. In very few MF patients, respiratory distress, disseminated intravascular coagulation, and multiorgan failure have been reported.

Hepatitis B viral load increases, with and without associated elevations in ALT and AST, have been reported in patients with chronic hepatitis B infections taking ruxolitinib. The effect of ruxolitinib on viral replication in patients with chronic hepatitis B virus is unknown. A rare disease called PML has been reported during treatment with ruxolitinib. It is important to note that PML and infections are complications associated with MF that have been previously described in the absence of ruxolitinib. Additionally, non-melanoma skin cancers, including basal cell, squamous cell, and a rare and aggressive type of skin cancer called Merkel cell carcinoma have been reported in patients who took ruxolitinib; it is unknown whether this was due to ruxolitinib treatment.

In the presence of potent CYP3A4 inhibitors (see Appendix D), there is the possibility of increased exposure to ruxolitinib. A dose adjustment for the 15 mg BID ruxolitinib/placebo group is required when coadministered with potent CYP3A4 inhibitors (see Section 7.2.1.2). No dose adjustment of ruxolitinib is required for participants assigned to 5 mg BID ruxolitinib/placebo.

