7. STUDY TREATMENT

7.1. Study Treatment Administered

Ruxolitinib 5 mg tablets or matching placebo will be administered BID approximately 12 hours apart (morning and night) without regard to food/feeding. One or 3 tablets will be administered per dose, depending on the assigned treatment arm (ie, 1 tablet per dose for 5 mg ruxolitinib/placebo and 3 tablets per dose for 15 mg ruxolitinib/placebo).

Initially, ruxolitinib will be administered through an enteric feeding tube as follows:

- Suspend tablet(s) in approximately 40 mL of water with stirring for approximately 10 minutes.
 - For 5mg BID ruxolitinib/placebo treatment assignment: one 5 mg tablet in 40 mL water
 - For 15 mg BID ruxolitinib/placebo treatment assignment: three 5 mg tablets in 40 mL water

Within 6 hours after the tablet has dispersed, the suspension can be administered through the enteric feeding tube using an appropriate syringe.

• The tube should be rinsed with approximately 75 mL of water.

Dosing of ruxolitinib during prone positioning is permitted if consistent with institutional policy. If enteric medication administration is not possible during prone positioning, administration of ruxolitinib should occur before or after proning sessions, adhering as closely to the BID dosing schedule as possible.

If a participant is extubated during the study and is able to take oral medication, study drug may be administered orally with water, without regard to food.

The recommended duration of treatment is up to 14 days. Beginning on Day 15, treatment may be extended another 14 days (through Day 28) at the discretion of the investigator, if the benefits of treatment outweigh the risks, and with approval from the sponsor medical monitor.

Dose reductions or interruptions for any toxicity attributed to ruxolitinib are permitted to allow the participant to continue on study treatment (see Section 7.6.2).

Table 5 presents the study treatment information.

Table 5:Study Treatment Information

Investigational/Control Drug	Pharmaceutical Dosage Form	Route of Administration	Supply Type
Ruxolitinib 5 mg	Tablet	Enteric feeding tube or oral	Double-blind supply; bottles
Placebo for 5 mg ruxolitinib	Tablet	Enteric feeding tube or oral	Double-blind supply; bottles

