7.4. Treatment Blinding

Participants, investigator staff, persons performing the assessments, and the Incyte study team will remain blind to the identity of the treatment from the time of randomization until database lock using the following methods: (a) randomization data will be kept strictly confidential until the time of unblinding and will not be accessible by anyone else involved in the study, and (b) the identity of the treatments will be concealed by the use of study treatments that are all identical in packaging, schedule of administration, appearance, taste, and odor.

Unblinding will occur in the case of participant emergencies and at the conclusion of the study. If the investigator feels that unblinding prior to completion of the treatment period is clinically indicated, consult the Medical Monitor.

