### **3.1. Randomization**

Participants will be randomized 2:2:1 to receive ruxolitinib 5 mg BID, 15 mg BID, or matching-image placebo for an initial period of 14 days. Placebo participants will be randomized 1:1 to receive either the 5 mg BID image or the 15 mg BID image. Block randomization with stratification for ARDS severity (severe [ $\text{PaO}_2/\text{FiO}_2 \leq 100$ ] vs mild/moderate [ $\text{PaO}_2/\text{FiO}_2 > 100$  and  $\leq 300$ ]) and investigational site will be used.

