### **3.3. Sample Size Considerations**

The primary endpoint of this study is the proportion of participants who die due to any cause through Study Day 29. The primary endpoint will be tested for each ruxolitinib treatment group using a logistic regression model including treatment (ruxolitinib vs placebo) and ARDS severity (severe [ $\text{PaO}_2/\text{FiO}_2 \leq 100$ ] vs mild/moderate [ $\text{PaO}_2/\text{FiO}_2 > 100$  and  $\leq 300$ ]) as fixed covariates and investigational site as a random (intercept) effect. For placebo randomized 2:2:1 (ruxolitinib 5 mg BID:ruxolitinib 15 mg BID:placebo) assuming a 40% mortality rate for ruxolitinib versus 60% for placebo, a sample size for a pairwise comparison of 100 placebo and 200 ruxolitinib participants (with 500 participants total) will achieve approximately 83% power to detect a statistically significant difference with a nominal 1-sided Type I error of 1.436968%.

Estimated power and Type I error for various scenarios, based on a simulation study of 1000 study replications, are provided in [Table 2](#).

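### At about 21 placebo participants per tablet image, the planned Fisher test cannot show that the images agree; report the difference with a confidence interval and add a tablet-matched supportive model

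*SAP*

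**What the plan says.** Protocol 7.1 sets the tablet count by arm: "One or 3 tablets will be administered per dose, depending on the assigned treatment arm". No double-dummy is described. SAP 3.1 gives the allocation: "Participants will be randomized 2:2:1 to receive ruxolitinib 5 mg BID, 15 mg BID, or matching-image placebo", and then "Placebo participants will be randomized 1:1 to receive either the 5 mg BID image or the 15 mg BID image". Some site instructions depend on the image. On potent CYP3A4 inhibitors, Protocol 5.6 says: "No dose adjustment of ruxolitinib is required for participants assigned to 5 mg BID ruxolitinib/placebo", while Protocol 7.2.1.2 applies a rule to the 15 mg ruxolitinib/placebo arm only. The blinding statement in Protocol 7.4 describes "study treatments that are all identical in packaging, schedule of administration, appearance, taste, and odor".

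The analysis compares each dose with all placebo participants, whatever their image (SAP 3.3, 7.1 and 7.3.1). SAP Table 3 has no comparison restricted to the matching image. The text after Table 3 compares mortality and loss to follow-up between the images "to determine if the rate is consistent across the 2 treatment images", by Fisher's exact test overall and within ARDS severity. Other endpoints may be compared by image but are not named. No significance level, margin, confidence interval or consequence is attached. SAP 3.3 puts the final analysis at 211 participants.

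**The concern.** The stated purpose is to find out whether the two images agree. A test of no difference can detect disagreement if it is large enough, but it supports agreement only if it would probably have detected a gap that matters. With roughly 21 participants per image that condition fails, and no interval is planned that would show the reader how large a gap remains possible.

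Each primary comparison, including the 15 mg comparison that is now tested first (SAP 3.2), takes about half of its controls from the other image. If placebo mortality differed between images, pooling would move the control rate away from that of the matching image by half the gap. The documents give no sign of such a gap. The difficulty is that the planned check would probably not reveal one, and its result could be read as reassurance.

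**Working it through.** **Inputs.** Allocation 2:2:1 and placebo split 1:1 (SAP 3.1); 211 participants (SAP 3.3); design mortality 60% on placebo and 40% on ruxolitinib (SAP 3.3). Assumed: two-sided 5% for the image test, ratios held exactly, and severity strata of equal size. The last appears in the SAP only as a simulation input.

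**1. The plan's own figure.** The documents give no power for the image test. To confirm the rates and sample sizes, I reproduced the stated 83% for 100 placebo versus 200 ruxolitinib at one-sided 0.01436968 (z = 2.187).
- Pooled rate (100×0.6 + 200×0.4)/300 = 0.467. Null SE = √[0.467×0.533×(1/100 + 1/200)] = 0.0611. Alternative SE = √(0.24/100 + 0.24/200) = 0.0600.
- Power = Φ[(0.20 − 2.187×0.0611)/0.0600] = 86.6%. With a continuity correction of ½(1/100 + 1/200) = 0.0075 it is 83.7%, which agrees with the plan.

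**2. Image sizes at 211.** Placebo 211/5 = 42.2, so about 21 per image. Each ruxolitinib arm 211×2/5 = 84.4, so about 84.

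**3. Power of the Fisher test.** Power is the sum of Bin(x; n₁, p₁)·Bin(y; n₂, p₂) over all tables with two-sided Fisher p ≤ 0.05.

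| Per image | 60% v 60% | 60% v 50% | 60% v 40% | 60% v 30% |
|---|---|---|---|---|
| 21 v 21 | 2.0% | 4.8% | 15.1% | 36.0% |
| 50 v 50 (planned size) | 3.2% | 13.4% | 46.2% | 82.9% |

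- At 21 v 21, 80% power needs a gap of about 46 points (60% v 14%).
- Splits of 18/18, 18/24, 20/22 and 24/24 give 16% to 21% for 60% v 40%, so the result does not depend on an exact 21/21.
- Within severity, 60% v 40% gives 5.4% (10 v 10), 7.4% (11 v 11) and 9.8% (10 v 11).
- If the image with more deaths has 11 to 17 of 21, significance needs a difference of at least 8 deaths, an observed gap of 8/21 = 38 points.

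**4. Precision.** At 60% in both images the 95% half-width is 1.96×√(2×0.24/21) = 0.296, about 30 points. With identical results (13/21 in each) the Newcombe interval is −27 to +27 points.

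**5. What a missed gap could do (illustration only).** Suppose mortality is 60% in the 15 mg arm and in its own placebo image, and 80% in the other image. Pooled placebo is then (60 + 80)/2 = 70%, which is 10 points too high.
- Overall rate (42×0.70 + 84×0.60)/126 = 0.633. Null SE = √[0.633×0.367×(1/42 + 1/84)] = 0.0911. Alternative SE = √(0.24/84 + 0.21/42) = 0.0886.
- Chance of declaring 15 mg superior at one-sided 2.5%: Φ[(0.10 − 1.96×0.0911)/0.0886] ≈ 19%. Fisher power for 60% v 80% at 21 v 21 is also 19%.

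**6. Cost of matching on tablet count.** SE of the log odds ratio = √[1/(n₀×0.24) + 1/(84×0.24)], which is 0.386 with pooled placebo (n₀ = 42) and 0.498 with matched placebo (n₀ = 21). By the formula in step 1 without the correction, power for 60% v 40% at one-sided 2.5% is about 57% pooled and 38% matched.

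**The case against.** The strongest reply is that the masking that matters is intact. Under 2:2:1 with placebo split 1:1, active to placebo is 4:1 within each tablet count. Staff who see one tablet know the dose level but cannot tell that the participant is on placebo. A reader might infer that half of the control group is unblinded; the documents do not support that. Nor do they show bias in the primary endpoint. All-cause death needs no judgement, and a difference between images would have to arise through care, dosing rules, treatment extension or dropout, none of which is shown to have differed enough. This part of the reply stands.

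A reader might also see a contradiction with the blinding section. That statement covers treatments "all identical in packaging, schedule of administration, appearance, taste, and odor". Tablet count is not among the listed attributes, and the one- and three-tablet images are stated openly elsewhere. Enrollment has been halted, so rewording that section would change no conduct.

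It can also be said that no decision rests on the test, since pooling is unconditional, and that mortality is not the only thing compared: loss to follow-up, the severity subgroups and optional further endpoints are covered as well. Both are true. But the further checks use the same or fewer placebo participants, and a test with no decision attached still needs wording that its data can support.

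Finally, the matched model has low power and cannot settle the matter either. That is correct, and is why it can be only supportive. The image comparison was added after FDA comments (SAP 11.2.1), which is a reason to keep the Fisher test and supplement it.

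**Conclusion.** The point holds as one about interpretation. At about 21 per image, a 20-point gap in placebo mortality, as large as the effect the trial was designed to detect, would be missed about 85% of the time, and a 30-point gap about 64% of the time. The interval for the difference spans roughly 30 points either way. Non-significance therefore says very little about consistency. It would be too strong to say that non-significance is almost certain whatever the truth: that applies to small gaps, not to one of 30 points.

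The figures assume that the allocation ratios held at 211, 60% mortality in one image, and a two-sided 5% test; the within-severity figures also assume equal strata. Actual counts by image are not given. The finding does not impugn the pooled primary analysis and does not show that any endpoint is biased. It is a modest, inexpensive improvement to the plan.

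**What to change.** In SAP 7.3.3, while treatment codes are still closed:

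1. Keep the Fisher tests. Beside them report the between-image differences in 28-day mortality and in loss to follow-up with 95% confidence intervals (Newcombe, for example).
2. State that these results are descriptive and that a non-significant test does not establish consistency.
3. Add one supportive row to Table 3: the primary mortality model for each dose against placebo participants with the same tablet count, with the fallback already given in SAP 7.3.1 if the model does not converge. List it in Appendix A.
4. At most, name ventilator-free days and the ordinal scale as endpoints to be compared by image, so that the choice is not left open. Matched analyses of every secondary endpoint are not needed.

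The pooled primary analysis and Protocol 7.4 stay as they are. The cost is a few sentences, extra columns in planned table 2.1.7 and one supportive table, with no new data. The downside is the matched model's lower precision (0.50 against 0.39 on the log odds scale), so it should not be read as a second test of efficacy.

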## 7.4. Analysis of the Secondary Efficacy Parameters

### 7.4.1. In-Hospital Outcomes

The number of ventilator-free, ICU-free, oxygen-free, vasopressor-free, and hospital-free calendar days between Study Days 2 and 29 (inclusive) will be derived using the rules as outlined in [Table 4](#). Note that qualifying vasopressor medications (ie, ATC Class C01CA - adrenergic and dopaminergic agents) will be determined through blinded review of concomitant medications, with the list of medications qualifying as vasopressors included as a note to file prior to final database lock.

Outcome-free days between Days 2 and 29 will be summarized descriptively (mean, mean, standard deviation) with treatment-group statistical comparisons performed using a Kruskal-Wallis test. Participants with missing data that do not permit evaluation for all 28 days, but are known to be alive at Day 29, will have each such day treated as not event-free. Participants who die prior to or on Day 29 will have 0 assigned days for each event-free endpoint. Participants for whom Day 29 survival status cannot be ascertained will be missing from the analysis.

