- BMI at baseline: $\geq 30 \text{ or } < 30$

In addition, the 28-day mortality rates and participants lost to follow-up in the placebo group will be compared by the placebo image assigned (5 mg BID and 15 mg BID) to determine if the rate is consistent across the 2 treatment images. Additional endpoints may also be compared within placebo-assigned participants by treatment image.

The 9-point ordinal scale will be tabulated by visit. The odds of observing an improvement in the 9-point ordinal scale on Days 15 and 29 will be analyzed using a POM, which will include treatment group, ARDS severity (mild/moderate vs severe), and gender (male or female) as fixed covariates and investigational site as a random effect. The odds ratio for treatment group (ruxolitinib vs placebo) estimated from the POM can be interpreted as a summary of the odds ratios obtained from separate binary logistic regressions using all possible cutoff points of the ordinal outcome (eg, the cutoff of level 5, "Hospitalized, on non-invasive ventilation or high flow oxygen device" will combine levels 0, 1, 2, 3, and 4 versus combined levels 5, 6, 7, and 8).

The assumption of POM is that the effect of treatment is identical across all possible cutoff points of the ordinal outcome.

The number and percentage of participants with a 1-point improvement at Days 15 and 29 will be tabulated and summarized by treatment group. A logistic regression model will be used to model the probability of such an improvement that includes treatment group, ARDS severity (mild/moderate vs severe), and gender (male or female) as fixed covariates and investigational site as a random effect. A similar summary will be used for two-point improvements at Days 15 and 29.

The time from randomization to first improvement in the COVID-19 9-point ordinal scale will be derived. Participants who never improve on-study will be censored at their last assessment or Study Day 29, whichever is earlier. A Kaplan-Meier analysis will be used to describe the time to first improvement.

Endpoints related to clinical outcomes are defined in Table 11. Outcome-free days between Days 2 and 29 will be summarized descriptively (mean, mean, standard deviation) with treatment-group statistical comparisons using a Kruskal-Wallis test.

Endpoint	The Number of Study Days That a Participant Was Alive and
Ventilator-free days	did not require mechanical ventilation. ^a
ICU-free days	is out of the ICU. ^a

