### 7.1. General Considerations

Unless otherwise stated, the strata identified in the randomization process will be used in all efficacy analyses. For statistical analyses of the primary and secondary endpoints, separate models will be fit for the ruxolitinib 5 mg BID versus placebo and ruxolitinib 15 mg BID versus placebo comparisons.

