### 7.3.3. Sensitivity and Supportive Analyses for Primary Endpoint

A sensitivity analysis will be conducted in the ITT population, in which nonevaluable participants will be treated as deaths. The primary endpoint will be analyzed using the PP population as a sensitivity analysis to the ITT analysis. In addition, a tipping point analysis will be performed to measure the robustness of the treatment effect under assumptions for participant dropout. The tipping point analysis will use an unstratified 2-sample test of proportion, modifying dropouts within the compared ruxolitinib treatment group as having died and placebo participants as having lived to determine if and at what point in this imputation a statistically significant treatment effect under the base assumptions will lose statistical significance.

Analyses related to the primary endpoints are delineated in [Table 3](#).

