#### 7.4.2.1. Proportional Odds Model for COVID-19 9-Point Ordinal Scale

The odds of observing an improvement in the 9-point ordinal scale on Days 15 and 29 will be analyzed using a proportional odds model for the ITT and PP populations. The odds of observing a better category on the ordinal scale (lower number) will be analyzed separately at Days 15 and 29. The model will include treatment group and ARDS severity (severe vs mild/moderate) as fixed covariates and investigational site as a random effect.

As a sensitivity analysis to the proportional odds model, a Cochran-Mantel-Haenszel test for differences in treatment groups for the 9-point ordinal scale at Days 15 and 29, stratifying for ARDS severity, will also be provided.

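### The event-free-day endpoints are compared by a Kruskal-Wallis test that names no stratum; a rank test stratified by ARDS severity would follow the SAP's default and recover a little power

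*SAP*

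**What the plan says.** - **Test.** SAP 7.4.1 counts the days from Day 2 to Day 29 that are free of ventilator, ICU, oxygen, vasopressor and hospital. A participant who dies by Day 29 scores 0 on all five. The groups are compared by "treatment-group statistical comparisons performed using a Kruskal-Wallis test". Protocol 12.4.1 has "treatment-group statistical comparisons using a Kruskal-Wallis test". Neither names a stratum or covariate.
- **Randomization.** SAP 3.1: "Block randomization with stratification for ARDS severity", together with investigational site.
- **Default.** SAP 7.1: "Unless otherwise stated, the strata identified in the randomization process will be used in all efficacy analyses". The same section adds that "separate models will be fit for the ruxolitinib 5 mg BID versus placebo and ruxolitinib 15 mg BID versus placebo comparisons".
- **How the SAP marks its choices elsewhere.** In 7.3.3: "The tipping point analysis will use an unstratified 2-sample test of proportion". In 7.4.2.1, the Cochran-Mantel-Haenszel test for the ordinal scale is described as "stratifying for ARDS severity, will also be provided".
- **Level.** SAP 3.2 tests secondary efficacy variables two-sided at 0.05, without multiplicity adjustment.

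**The concern.** A standard Kruskal-Wallis test has no stratum term. As written, neither randomization factor enters the comparison of these five secondary endpoints, and 7.4.1 does not say whether that is intended. A programmer could apply the 7.1 default or the literal test, and the two can give different p-values.

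The section also leaves open whether the test spans three arms or is done pairwise. Kruskal-Wallis permits both. SAP 7.1 speaks of separate models for each dose against placebo, and Protocol 12.4.1 makes pairwise comparison with placebo its general rule.

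Because every death scores 0, a factor that predicts death also moves the ranks on all five endpoints. If severity is such a factor, an unstratified test leaves its variation in the error term. SAP 3.3 fixes the final analysis at 211 participants, well short of the planned 500, so recoverable precision is worth having. What is at stake is efficiency and clarity, not validity.

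**Working it through.** **1. The plan's own figure.** The documents give no power figure for event-free days. Their only one, about 83%, belongs to the primary endpoint: 100 vs 200 participants, mortality 60% vs 40%, one-sided alpha 0.01436968 (critical z about 2.187).

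- Pooled SE = √[(140/300)(160/300)(1/100 + 1/200)] = 0.0611. Unpooled SE = √[0.24(1/100 + 1/200)] = 0.0600.
- Power = Φ[(0.20 − 2.187 × 0.0611)/0.0600] = 86.6%, close to the 0.868 in SAP Table 2.
- A continuity correction of 0.5 × 0.015 = 0.0075 gives 83.7%. Exact Fisher power is 83.2%. Both reproduce the 83%.

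This does not bear on the event-free-day test.

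**2. Group sizes.** 211 participants at 2:2:1 give 211 × 1/5 ≈ 42 placebo and 211 × 2/5 ≈ 84 per ruxolitinib dose.

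**3. The two tests.** With two groups, Kruskal-Wallis is the two-sided Wilcoxon rank-sum test. The van Elteren test ranks within each severity stratum *h*. With n_h participants, m_h of them on ruxolitinib, and rank sum W_h:

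- Z = Σ[(W_h − m_h(n_h + 1)/2)/(n_h + 1)] / √Σ[V_h/(n_h + 1)²]
- V_h = m_h(n_h − m_h)/[n_h(n_h − 1)] × Σ(r − r̄)², which allows for ties

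**4. Assumptions.** These are not in the documents except where stated.

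- Half the participants are severe (the proportion in the note to SAP Table 2), with exact balance between arms within stratum.
- Placebo mortality averages 60% over the strata.
- The within-stratum mortality odds ratio is (0.4/0.6)/(0.6/0.4) = 4/9, from the planned 40% vs 60%.
- Survivors' days follow a rounded beta distribution on 0 to 28. The mean is 14 in mild/moderate participants and lower in severe participants by 0, 10% or 20% of 28 days in (a), (b) and (c). Treatment acts on mortality only.
- 4000 trials per cell, two-sided 0.05, with both tests run on the same data.

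**5. Results** (KW = Kruskal-Wallis, VE = van Elteren)

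| Placebo mortality, mild/moderate : severe | Placebo : ruxolitinib | Type I error KW / VE | Power KW / VE |
|---|---|---|---|
| (a) 60% : 60% | 100 : 200 | 0.046 / 0.045 | 85.7% / 85.5% |
| (a) 60% : 60% | 42 : 84 | 0.048 / 0.047 | 49.0% / 48.7% |
| (b) 50% : 70% | 100 : 200 | 0.046 / 0.050 | 80.5% / 81.3% |
| (b) 50% : 70% | 42 : 84 | 0.046 / 0.051 | 43.7% / 45.2% |
| (c) 40% : 80% | 100 : 200 | 0.033 / 0.050 | 65.2% / 69.6% |
| (c) 40% : 80% | 42 : 84 | 0.026 / 0.047 | 29.9% / 35.6% |

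The severity odds ratios for death in placebo are 1 in (a), (0.7/0.3)/(0.5/0.5) = 2.3 in (b), and (0.8/0.2)/(0.4/0.6) = 6 in (c). Compare within rows only: the fixed within-stratum odds ratio gives a smaller overall effect as the strata diverge. The Monte Carlo standard error is about √(0.3 × 0.7/4000) = 0.007 per power estimate near 30%.

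**6. Other assumptions, same sizes.** Severity odds ratios of 2, 3 and 4 were tried at one-sided 2.5%, with 40% of survivors having no free days and 2000 replicates. Power moved from 0.26 to 0.26, 0.22 to 0.23, and 0.20 to 0.22. With 20% to 60% of survivors at zero, the largest gain was about 3 points. The standard error is about √(0.22 × 0.78/2000) = 0.009 per estimate, so the smaller gains are within noise. A further run at two-sided 0.05 again gave 0 to about 3 points, with Kruskal-Wallis Type I error about 0.036 to 0.039 when severity was strongly prognostic.

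**7. Site as a stratum.** The number of sites is not stated. With the 10 sites assumed in the note to SAP Table 2, there are 20 site-by-severity cells. A pairwise comparison then has 126/20 = 6.3 participants per cell, of whom 42/20 = 2.1 are placebo.

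**The case against.** **The rule in 7.1 has an exception clause.** A reader might infer that 7.4.1 contradicts an absolute rule. The documents do not support that. Naming a specific test without strata, identically in Protocol and SAP, can be read as the permitted exception. This stands: the point is an unmarked departure, not a contradiction. It remains a point because 7.3.3 shows that the SAP labels an unstratified test when it intends one.

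**These endpoints are not alone.** A reader might take them as the only efficacy analyses without the randomization strata. They are not. The tipping-point test is unstratified, the overall Fisher comparison of the placebo images in 7.3.3 has no strata, and the SOFA component tests in 7.4.3.2 stratify by baseline organ score instead.

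**Severity imbalance.** A reader might fear sizeable chance imbalance with about 42 placebo participants. Blocked randomization within severity is designed to limit it. Incomplete site-by-severity blocks could leave some, but nothing in the documents shows that it would be large. The case for stratifying does not rest on it.

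**Severity may not be prognostic here.** The documents give no effect size, and the simulation behind SAP Table 2 set it to none. That is a modelling assumption, not evidence, and the primary model adjusts for severity. If there is no effect, stratifying gains nothing, but it costs at most 0.3 points in row pair (a).

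**The stakes are low.** These are secondary endpoints without multiplicity control. This stands too.

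**Conclusion.** The point holds as one of efficiency and clarity. The Kruskal-Wallis test is valid: its simulated Type I error never exceeded 0.05, and it fell to about 0.03 in the strongest severity scenario, under exact balance within strata.

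At about 84 vs 42, the power lost by leaving severity out is 0 to about 3 points in most assumed scenarios. It is about 6 points (35.6 − 29.9 = 5.7) if placebo mortality is 40% vs 80% by stratum. These figures rest on assumed severity effects and an assumed distribution of survivors' free days.

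The documents do not support a stronger conclusion, such as an invalid test or a threat to the primary result. Stratifying is worth doing because it uses a factor the trial already randomizes by and costs next to nothing when that factor has no effect.

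**What to change.** In SAP 7.4.1, replace the Kruskal-Wallis test with a two-sided van Elteren test (Cochran-Mantel-Haenszel row mean scores with modified ridits), stratified by ARDS severity as randomized. Do it separately for 5 mg BID vs placebo and 15 mg BID vs placebo. State that site is not used as a stratum because the site-by-severity cells would probably be sparse. This is needed because a severity-only test is still a partial departure from the 7.1 default.

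If the Kruskal-Wallis test is kept, say in 7.4.1 that it is an intended unstratified exception to 7.1 and that it is done pairwise.

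Cost: one sentence in 7.4.1, one entry in SAP 11.1 because Protocol 12.4.1 names the same test, and one changed procedure call. No new data are needed. The change should be made before unblinding.
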